4.4.1.1 Serious Adverse Event (SAE)

An SAE is defined as any untoward medical occurrence that at any dose:

- 1. Results in DEATH.
- 2. Is LIFE THREATENING.

The term "life threatening" refers to an event in which the patient was at risk of death at the time of the event; it does not refer to an event that hypothetically might have caused death if it were more severe.

- 3. Requires inpatient HOSPITALIZATION or prolongation of existing hospitalization.
- 4. Results in persistent or significant DISABILITY/INCAPACITY.

- 5. Leads to a CONGENITAL ANOMALY/BIRTH DEFECT.
- 6. Is an IMPORTANT MEDICAL EVENT that satisfies any of the following:
 - May require intervention to prevent items 1 through 5 above.
 - May expose the patient to danger, even though the event is not immediately life threatening or fatal or does not result in hospitalization.
- 7. Sight-threatening events.

PTEs that fulfill 1 or more of the serious criteria above will also be considered as SAEs and should be reported and followed up in the same manner.

4.4.1.2 Sight-Threatening Adverse Event

The *sight-threatening AE* is defined as any serious ocular AE that places the subject at immediate risk of permanent vision loss in either the analysis eye or the fellow eye. In this study, the following serious ocular AEs will be reported as sight-threatening AEs if it meets one or more of the following criteria:

- It caused a decrease in visual acuity of > 30 letters (compared with the last assessment of visual acuity at the last visit) lasting > 1 hour
- It caused a decrease in visual acuity to the level of Light Perception or worse lasting > 1 hour
- It required surgical intervention (e.g., conventional surgery, vitreous tap or biopsy with intravitreal injection of anti-infectives, or laser or retinal cryopexy with gas) to prevent permanent loss of sight
- It is associated with severe intraocular inflammation (i.e., 4+ anterior chamber cell/flare or 4+ vitritis)

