## 10.1.3 Sight-threatening Events

An event is considered sight-threatening and should be reported as an SAE if it meets one or more of the following criteria:

- It caused a decrease in visual acuity of >30 letters (compared with the last assessment of visual acuity at the last visit) lasting >1 hour
- It caused a decrease in visual acuity to the level of Light Perception or worse lasting >1 hour
- It required surgical intervention (e.g., conventional surgery, vitreous tap or biopsy with intravitreal injection of anti-infectives, or laser or retinal cryopexy with gas) to prevent permanent loss of sight
- It is associated with severe intraocular inflammation (i.e., 4+ anterior chamber cell/flare or 4+ vitritis)
- In the opinion of the investigator it may require medical intervention to prevent permanent loss of sight

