9 SAFETY ANALYSES

The safety-related measures collected in this study include systemic and ocular AEs, corrected and uncorrected distance visual acuity, slit-lamp biomicroscopy, dilated fundus examinations, and IOP. The Safety population will be used for all safety summaries.

All the safety-related measures will be summarized descriptively. Except systemic AEs, which will be summarized at the subject level, all the other safety-related measures, including ocular AEs, will be summarized for the analysis eyes and fellow eyes separately.

9.1 **Pre-treatment Events (PTEs) and Adverse Events (AEs)**

PTEs and AEs are defined in Section 4.4.1. PTEs and treatment-emergent AEs (TEAEs) will be summarized separately.

In the overall AE summaries, subjects with any AE(s) will be tabulated by the following types of AEs:

- AEs
- SAEs
- Related AEs
 - AEs related to the study medication
 - AEs related to artificial tears
 - AEs related to study procedures
- AEs leading to premature discontinuation
- Sight threatening AEs
- Case of special interest
- Death

The above summaries will be repeated for ocular AEs in the analysis eye, ocular AEs in the fellow eye, and non-ocular AEs, respectively.

Besides the overall AE summaries listed above, AEs will be tabulated by SOC and PT. A subject who experienced multiple AEs within a SOC or PT will be counted only once for that SOC or PT, respectively. SAEs, related AEs, and serious related AEs will be tabulated similarly. Ocular and systematic AEs will also be summarized separately.

In addition, AEs will be tabulated by the following categories:

- SOC, PT, and maximal severity
- SOC, PT, and relationship (related to study medication, study procedure, or artificial tears)
- SOC, PT, maximal severity, and relationship (related to study medication, study procedure, or artificial tears)

Ocular AEs will be summarized for the analysis eye and fellow eye separately. Any ocular AE that occurred simultaneously to both eyes will be counted once for both the analysis eye and the fellow eye. Sight-threatening AEs and cases of special interest will be summarized by type of events specified in Section 4.4.1.2 and Section 4.4.1.3.

AEs, AEs leading to discontinuation, SAEs, sight-threatening AEs, case of special interest, and death, if any, will be listed separately.

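### SAP 4.4.1.2 lists four of the five sight-threatening criteria in protocol version 4.0 section 10.1.3, so an event meeting only the fifth would be missing from the sight-threatening outputs

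*SAP*

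**What the plan says.** Protocol section 10.1.3 gives the reporting rule: "An event is considered sight-threatening and should be reported as an SAE if it meets one or more of the following criteria". Five alternatives follow, and the last rests on clinical judgement: "In the opinion of the investigator it may require medical intervention to prevent permanent loss of sight".

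SAP section 4.4.1.2 opens with a general description, "any serious ocular AE that places the subject at immediate risk of permanent vision loss in either the analysis eye or the fellow eye", and then gives the working rule: "the following serious ocular AEs will be reported as sight-threatening AEs if it meets one or more of the following criteria". Four criteria follow. The last is "It is associated with severe intraocular inflammation (i.e., 4+ anterior chamber cell/flare or 4+ vitritis", after which the SAP moves on to cases of special interest (4.4.1.3).

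SAP section 9.1 uses this definition. Its overall AE summary has a sight-threatening line. For the detailed table, "Sight-threatening AEs and cases of special interest will be summarized by type of events specified in Section 4.4.1.2 and Section 4.4.1.3". For listings, "AEs, AEs leading to discontinuation, SAEs, sight-threatening AEs, case of special interest, and death, if any, will be listed separately".

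SAP section 4.4.1.1 has "Sight-threatening events" as item 7 of its definition of a serious adverse event.

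SAP section 1 says that the plan applies to protocol version 3.0 of 07 April 2017. The protocol supplied is version 4.0 of 23 March 2018.

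**The concern.** The SAP promises dedicated sight-threatening outputs but fills them with a narrower definition than the current protocol uses. The missing criterion is the only one of the five that does not require a measured loss of acuity, surgery or severe intraocular inflammation. It is the route by which a threat to sight that may need medical treatment enters the category before one of those has occurred. Protocol section 4.0 names corneal ulceration with a risk of perforation among the complications in this population, and ocular safety is a secondary objective in both documents.

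What is at stake is agreement between the protocol's category and the table that carries its name. A reader of the study report would take the sight-threatening count to follow the protocol definition, and by the SAP's stated rule it would not.

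**Working it through.** No sample size, power or error rate is involved, so the check compares the two texts.

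**Step 1. Match the criteria.**

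| Criterion (paraphrased) | Protocol 10.1.3 | SAP 4.4.1.2 |
|---|---|---|
| Acuity loss of more than 30 letters for more than 1 hour | yes | yes |
| Acuity down to Light Perception or worse for more than 1 hour | yes | yes |
| Surgery needed to prevent permanent sight loss | yes | yes |
| Severe intraocular inflammation (4+) | yes | yes |
| Investigator's opinion that medical intervention may be needed | yes | **no** |
| Total | 5 | 4 |

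The four shared criteria have the same thresholds. The SAP list runs straight into 4.4.1.3, with no sign of redaction or lost text.

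**Step 2. Apply the SAP rule to an event that meets only the fifth criterion.** It meets 0 of the SAP's 4 criteria. The working sentence requires at least one, so the event is not classed as sight-threatening.

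**Step 3. Follow it through SAP 9.1.**

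- Sight-threatening line of the overall summary, including its repeats by eye: not counted.
- By-type table built from 4.4.1.2: no row for it.
- Sight-threatening listing: not included.
- AE tables and AE listing: included.
- SAE tables and SAE listing: included, provided that it is reported as an SAE as protocol 10.1.3 requires.

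**Step 4. Look for a declared change.** SAP section 10 covers the FVA parameters, the LogMAR conversion, the CFS change categories and the added correlation analyses. None of these concerns the sight-threatening definition.

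**Step 5. Check the versions.** The SAP refers to version 3.0 and only version 4.0 is available. The fifth criterion may have been in version 3.0 and left out of the SAP, or it may have come in with version 4.0. The documents do not settle which. In either case the SAP does not match the current protocol.

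**Step 6. Compare the direction of the two rules.** In protocol 10.1.3, meeting a criterion makes the event reportable as serious. In SAP 4.4.1.2 the event must already be serious to qualify, while item 7 of SAP 4.4.1.1 makes sight-threatening events serious. The SAP wording is circular. If sites follow the protocol, every event that meets a criterion is already reported as an SAE, so the circularity excludes nothing.

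**The case against.** The strongest objection is that very little is lost. The event remains in the AE tables and listing. The protocol requires it to be reported as an SAE, and item 6 of SAP 4.4.1.1 separately covers important medical events that may need intervention. With 17 patients enrolled, anyone reading the SAE listing would see it. The study is exploratory and single-arm, and no safety measure is tested. All of this stands, and it limits the consequence to the sight-threatening label. A reader might infer that such events disappear from safety reporting, but the documents do not support that.

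It can also be said that the SAP's general description, with its reference to immediate risk of permanent vision loss, already covers these events. It may cover some of them. However, the working sentence requires a listed criterion, the table is built from the listed types, and immediate risk is a different test from a possible need for medical intervention. This part of the objection does not remove the mismatch.

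A third objection is that the SAP may have been faithful to version 3.0. That stands as to cause. A reader might infer that the SAP dropped a protocol criterion without declaring it, but without version 3.0 that cannot be shown.

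Finally, protocol 10.2.1.2 lists what is recorded for each event and names no sight-threatening flag and no field for the criterion met. This also stands. The documents do not show that the fifth criterion can be read directly from the database, so the cost of the fix has to allow for that.

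**Conclusion.** The mismatch is real: four of five criteria, with the investigator-opinion criterion absent from SAP 4.4.1.2 and the difference not declared in section 10. Under the SAP as written, an event meeting only that criterion would be missing from three outputs: the sight-threatening line, the by-type table and the listing. This assumes that the working sentence in 4.4.1.2 and the cross-reference in 9.1 are applied literally, and that no eCRF field following the protocol wording overrides them. The SAP describes no such field.

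The impact is low. No primary result or SAE count depends on the point. Two ways of enlarging it should be resisted. The missing share of the criteria list, one in five, says nothing about how often such events occur. Expressing one event as a percentage of the 17 enrolled patients says no more: the documents give no event rate, and SAP section 5.2 counts only treated patients with follow-up, so the denominator could be smaller. Whether any event would be affected is unknown.

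The circular seriousness wording is a secondary drafting matter, and would have an effect only if a site failed to report a qualifying event as serious.

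**What to change.** - Add the fifth criterion of protocol 10.1.3 to SAP 4.4.1.2 word for word.
- Add its row to the by-type summary in SAP 9.1. The overall line and the listing then follow from the definition.
- Update the protocol version cited in SAP section 1. If a narrower definition is intended, state it and justify it in SAP section 10 instead.
- Say how these events will be identified. If the eCRF has no field for the criterion, use the reason for seriousness that protocol 10.2.2 requires on the SAE form.
- As a tidy-up, reword 4.4.1.2 so that meeting a criterion makes the event serious, as in protocol 10.1.3, and remove the condition that it already be serious.

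The cost is one line of definition, one table row and a corrected version reference, with a possible review of SAE forms or a site query where the reason recorded is unclear. At this study size that is a small task.

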4.4.1.3 Case of Special Interest

The following cases are considered to be of special interest by the Sponsor:

• Overdose:

Administration of a quantity of a medicinal product exceeding the dose defined in the study protocol/otherwise specify overdose.

• Misuse of study product:

Situations in which the medicinal product is intentionally and inappropriately used not in accordance with the study protocol.

• Medication error:

Any unintentional error in the prescribing, dispensing, or administration of a medicinal product while in the control of the healthcare professional, patient or consumer.

• Abuse of study product:

Persistent or sporadic, intentional excessive use of medicinal products which is accompanied by harmful physical or psychological effects.

4.4.1.4 Adverse Event Leading to Discontinuation

An AE will be counted as an *AE leading to Discontinuation* if the Investigator selected "AEs" in the "Primary reason for discontinuation or withdrawal" checklist on the END OF STUDY eCRF and checked "Definitive discontinuation" in the "Action taken regarding study drug" checklist on the AE eCRF.

4.4.1.5 Ocular Adverse Events

An AE will be counted as an *ocular AE* if the Clinical Investigator selected "Right Eye" or "Left Eye" or "Both Eyes" under the "Location" on the AE eCRF.

4.4.1.6 Systemic Adverse Events

An AE will be counted as a *systemic AE* if the Clinical Investigator selected "Other" or with a missing value under the "Location" on the AE eCRF.

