## 5.1.2 Secondary Objectives

The secondary objectives are:

- To assess the signs and symptoms of keratitis and DED, and their changes overtime,
- To estimate the correlation between CFS changes over time and FVA changes over time,
- To estimate the correlation between CFS changes over time and OSI changes over time,
- To estimate the correlation between variance of OSI changes overtime and FVA parameters overtime.
- To estimate the correlation between OSI changes overtime and FVA parameters changes overtime
- To compare the time course of the CFS improvement vs the time course of FVA and OSI improvement (if any), respectively,
- To evaluate the ocular tolerability and overall ocular safety of IKERVIS® administered once daily in DED patients with severe keratitis at Month 3.

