## 12.6 AEs

Adverse events will be coded using the MedDRA dictionary. Frequencies and percentages will be provided of patients with treatment-emergent adverse events (TEAEs), serious TEAEs, and TEAEs causing premature discontinuation. An adverse event is treatment emergent if it occurs or worsens after the first dose of study treatment. Furthermore, frequencies will be given of patients with TEAEs as follows: 1) by system organ class, by system organ class and preferred term, 2) by system organ class, preferred term and maximal severity, 3) by system organ class, preferred term and strongest relationship, and 4) by system organ class, preferred term, maximal severity, and strongest relationship.

Separate analyses will be performed for ocular and systemic adverse events. Ocular AEs will be summarised for the analysis eye and the other eye separately.

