2.1.2 Secondary Objectives

The secondary objectives are:

- To assess the signs and symptoms of keratitis and DED, and their changes over time,
- To estimate the correlation between CFS changes over time and FVA changes over time,
- To estimate the correlation between CFS changes over time and OSI changes over time,
- To estimate the correlation between variance of OSI changes over time and FVA parameters over time.
- To estimate the correlation between OSI changes over time and FVA parameters changes over time
- To compare the time course of the CFS improvement vs the time course of FVA and OSI improvement (if any), respectively.
- To evaluate the ocular tolerability and overall ocular safety of IKERVIS® administered once daily in DED patients with severe keratitis at Month 3.

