2.2.2.2 Safety Evaluations

- Slit lamp examination and change from baseline at Months 1, 2 and 3.
- Uncorrected Distance Visual Acuity (UDVA) and change from baseline at Months 1, 2 and 3.
- Best Corrected Distance Visual Acuity (BCDVA) and change from baseline at Months 1, 2 and 3.
- Dilated fundus examination and change from baseline at Month 3.
- IOP and change from baseline at Month 3.
- Incidence and severity of ocular and systemic adverse events over the study period.

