4.4 Safety-Related Definitions

4.4.1 Adverse Event (AE)

Events reported on the AE electronic case report form (eCRF) will be assessed according to the amended FDA regulations 21 CFR Parts 312 and 320.

Under Protocol NVG16E128, an AE is defined as any untoward medical occurrence in a clinical investigation patient administered an investigational product; it does not necessarily have to have a causal relationship with the treatment. An AE will be considered as a *pre-treatment event* (PTE) if the AE occurred after the patient has signed informed consent to participate in the study but prior to administration of any study medication; it does not necessarily have to have a causal relationship with study participation. An AE will be considered as *treatment-emergent* if the AE occurred on or after the treatment start date up to the last study visit or worsened relative to pre-treatment state.

The severity of each AE will be graded by the Clinical Investigator as Mild (aware or unaware of event, but easily tolerated), Moderate (discomfort enough to cause interference with usual activity), or Severe (incapacitating; unable to work or perform usual activity). AEs will also be rated by the Investigator as to their causality/relationship to the study medication, to the Sponsor provided artificial tears, as well as to the study procedures (related vs. not related).

Each AE will be classified into a system organ classification (SOC) and coded to a preferred term (PT) using Medical Dictionary for Regulatory Activities (MedDRA, version v19.1 English, March 2016).

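### Adverse events with a blank Location count as systemic whatever their coded term, so the ocular AE tables can undercount ocular events and cannot overcount them by this route

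*SAP*

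**What the plan says.** SAP 4.4.1.5 makes an event ocular only when the investigator selected the right eye, the left eye or both under Location. SAP 4.4.1.6 makes an event systemic when the entry is Other "or with a missing value under the" Location item. Neither section uses the event term or its code.

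The code will exist. SAP 4.4.1 states: "Each AE will be classified into a system organ classification (SOC) and coded to a preferred term (PT"), using MedDRA version 19.1.

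The split feeds planned output. Protocol 12.6 says: "Separate analyses will be performed for ocular and systemic adverse events", with ocular events shown by eye, and gives no rule for a missing location. SAP 9.1 repeats the overall AE summary for ocular events in the analysis eye, ocular events in the fellow eye, and non-ocular events. SAP 2.2.2.2 lists as a safety evaluation: "Incidence and severity of ocular and systemic adverse events over the study period". Protocol 5.1.2 includes among the secondary objectives: "To evaluate the ocular tolerability and overall ocular safety of IKERVIS".

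**The concern.** The default overrides information that the database will hold. If eye irritation is recorded with no eye selected, its preferred term shows that it is ocular, yet the rule reports it as systemic. All that is unknown about such an event is which eye was affected.

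The default also favours the drug on the question that the safety objective asks. Elsewhere the SAP leans the other way: section 6.2.3 says that missing event dates are imputed conservatively. No reason is given for treating Location differently. With 17 patients enrolled, one reclassified patient would visibly change a percentage in the ocular tables.

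**Working it through.** The documents give no ocular AE rate, no count of missing Locations and no sample size calculation, so there is no figure of the plan's own to reproduce. The check is one of logic, followed by illustrative arithmetic.

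**Direction.** There are four cases under SAP 4.4.1.5 and 4.4.1.6:

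| Event is truly | Location recorded correctly | Location blank |
|---|---|---|
| Ocular | counted as ocular | counted as systemic (wrong) |
| Non-ocular | counted as systemic | counted as systemic |

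Only one cell is wrong, and it removes an ocular event. No blank can add one. The effect on ocular incidence is zero or downward.

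**Size per patient.** Inputs: n = 17 enrolled (SAP 3.1), and incidence counted as patients with at least one event (SAP 9.1).

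- Shift per patient whose only ocular event has a blank Location: 1/n = 1/17 = 5.9 percentage points. At the planned 30 completers it would be 1/30 = 3.3 points.
- Shift in overall ocular incidence for a patient who also has an ocular event with a recorded eye: 0.
- Example: a true 3/17 = 17.6% (exact 95% CI 3.8 to 43.4) would be reported as 2/17 = 11.8% (1.5 to 36.4).

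The denominator is an assumption. SAP 5.2 requires at least one dose and some follow-up, and SAP 3.1 lets enrolled patients leave after wash-out untreated. If the Safety population is below 17, the shift 1/n is larger than 5.9 points.

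**How often it might happen.** Two quantities must be assumed: p, the share of patients with an ocular AE, and m, the chance that all of such a patient's ocular events have a blank Location. Then:

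- expected patients lost from the ocular count = n × p × m
- probability of losing at least one = 1 − (1 − p × m)^n

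| p | m | Expected lost (n = 17) | Probability of at least one |
|---|---|---|---|
| any | 0 | 0 | 0 |
| 10% | 5% | 0.09 | 0.08 |
| 20% | 5% | 17 × 0.20 × 0.05 = 0.17 | 1 − 0.99^17 = 0.16 |
| 20% | 20% | 0.68 | 0.50 |
| 40% | 20% | 17 × 0.40 × 0.20 = 1.36 | 1 − 0.92^17 = 0.76 |

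The range runs from no effect to about one patient. Nothing in the documents says where in that range the trial lies.

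**The case against.** The strongest reply is that the harm is conditional and that there are safeguards on both sides of the rule. Before it, Protocol 11.1 runs logic checks that look for missing data, issues queries to the sites, and has the principal investigator review the forms for completeness. Protocol 13.1 adds source verification. Blanks are easy to find among 17 patients. After it, SAP 9.1 tabulates all AEs by system organ class and preferred term and lists them, so an eye term with no Location stays visible and total counts do not change. Safety is descriptive with no testing (SAP 6), and the rule is prespecified.

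Most of this stands, and it limits the point. It does not remove it. No section makes Location mandatory, and Protocol 10.2.1.2 does not name it among the items documented for each event. The overall tables show the event but do not correct the ocular tables. It might also be argued that the form could use a blank to mean non-ocular. The form is not available to check, but Other is already offered for that.

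A reader might infer three stronger things that the documents do not support:

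- That the trial does undercount ocular events. This needs an ocular event to reach the locked database with no Location, and no section shows one.
- That the by-eye AE tables are the main safety output. SAP 2.2.2.2 lists six safety evaluations, five of them examinations that do not depend on AE Location.
- That every affected event costs 5.9 points. This is so only for a patient with no other ocular event that has a recorded eye, and only if 17 is the denominator.

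**Conclusion.** The point holds as a defect in a stated rule. SAP 4.4.1.6 can take ocular events out of the ocular tables and cannot put any in, although the coded term would allow correct classification. The actual effect is unknown and may be zero. If the Safety population is 17, it is 5.9 percentage points of ocular incidence for each patient whose only ocular event has a blank Location. No test, sample size or primary endpoint depends on it, and total AE counts are unaffected. This is a minor improvement, worth making because it protects a stated ocular safety objective at almost no cost.

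**What to change.** Amend SAP 4.4.1.5 and 4.4.1.6 as follows:

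1. Query every AE with a blank Location before database lock, using the checks already described in Protocol 11.1.
2. Classify any blank that remains by its MedDRA code. Terms in the Eye disorders class, and ocular terms in other classes as confirmed by medical review, count as ocular. Only non-ocular terms count as systemic.
3. Report these ocular events in an 'eye not specified' row and include them in overall ocular incidence. Do not enter them in both eye tables: SAP 9.1 counts an event for both eyes only when it occurred in both, so double entry would assign a one-sided event to an unaffected eye.
4. State the number of AEs with missing Location, including when it is zero.

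The cost is a brief review of any blank records and one extra table row. MedDRA coding is already required, and no new data are collected. If no Location is blank, the results do not change and the question is closed.
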